#### **11.5.2.2 Responder Rate for Averaged Daily Pain Score**

ADPS responder rate, defined as the proportion of subjects with  $\geq 30\%$  and  $\geq 50\%$  reduction from baseline to Week 14, will be calculated. The cumulative distribution of reduction from baseline in ADPS will be provided as a continuous responder analysis.

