### **11.2 General Statistical Considerations**

The statistical package SAS® (Version 9.2 or higher) will be used to produce tables, figures, and listings.

Safety analysis set will be used for all safety and efficacy analyses and PK analysis set will be for all PK analyses. All analyses will be conducted by CrCL group (ie, moderate and severe renal function impaired patients group).

Missing weekly ADPS value will be imputed based on "nonfuture dependence" model using the pattern mixture approach under the missing not at random (MNAR) mechanism so that bad outcomes (greater weekly ADPS value) can be attributed to subjects who discontinued the trial before Week 14. Detail will be at Section 11.5.2.1 and in the SAP.

Raw data will be presented to the exact precision at which they were collected. For summary statistics, means and medians will be displayed to one more decimal place than was determined for raw data, dispersion statistics will have two more decimal places, and the minimum and maximum will be displayed to the same number of decimal places as the raw data.

Quantitative data will be tabulated with descriptive summary statistics: arithmetic mean, standard deviation (SD), median, minimum and maximum values, and number of observations. For categorical data, frequency tables will be provided.

Analysis for the change from baseline, including the shift table, will be conducted for the subjects who have an available baseline value and at least 1 post-randomization value.

PK analysis will be detailed in the PK analysis plan (PAP).

A detailed SAP and PAP describing the methodology to be used in the final analysis will be prepared before data unblinding. A change in the planned statistical analysis will require a protocol amendment only if it substantively alters the principal features of the protocol. Any deviations from the planned statistical analyses in the protocol will be fully described in the SAP and PAP.

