##### **11.5.2.1 Average Daily Pain Score**

Observed weekly ADPS and change from baseline will be summarized by CrCL group and week.

Missing weekly ADPS values will be imputed based on a multiple imputation (MI) method using “nonfuture dependence” model which is specified by the pattern mixture approach with shifting parameters under MNAR mechanism. The imputation method above will consider the reason for dropout together with the time of dropout for constructing the missing data pattern.

The statistical model used for the MI data generation will be the Markov Chain Monte Carlo method with adjustment for covariates (eg, age, sex) to produce a monotone pattern first, and then the imputation will continue using the Regression with Predictive Mean Matching method for the monotone pattern with the same set of covariates. The primary shifting parameter values corresponding to the three categories in the pattern mixture model will be chosen as (1.0, 1.0, 0.5) for dropouts due to AE, LOE and AOR, respectively, and the corresponding shifting amount of the weekly ADPS imputed at first missing week is given by  $(1.0, 1.0, 0.5) * RSD * U(0,1)$  where  $U(0,1)$  is a random variable

from a uniform distribution with a range of 0 to 1, and RSD is the residual SD at first missing week after imputation. The imputed value will be replaced with 10 (the maximal ADPS score) when the imputed value of ADPS score is over 10. Additionally, for dropouts due to LOE, the imputed values will be bound so that a subject's imputed weekly ADPS after discontinuation cannot be better than that subject's baseline ADPS. Each complete imputed dataset will be analyzed using the repeated measures analysis with week as the fixed effect, week as the repeated effect, and baseline ADPS as a covariate to provide LS mean in weekly ADPS at each week. The results of the analysis from each complete imputed dataset will be combined using Rubin's rule.

Sensitivity analyses will include following:

- Repeated measures analysis using observed data only
- ANCOVA using Baseline Observation Carried Forward
- ANCOVA using LOCF

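### Does Section 11.5.2.2 have to say which ADPS values decide responder status when Week 14 is missing?

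*Combined protocol and SAP*

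**What the plan says.** Section 11.5.2.2 defines two responder rates by percentage reduction in ADPS ("reduction from baseline to Week 14, will be calculated") and plans a cumulative distribution of the reduction. It names no data source and gives no rule for a missing Week 14 value.

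The missing-data rule stands in Section 11.2, General Statistical Considerations: "Missing weekly ADPS value will be imputed based on" a nonfuture-dependence pattern mixture model. Its stated purpose is that bad outcomes "can be attributed to subjects who discontinued the trial before Week 14". The section adds: "Detail will be at Section 11.5.2.1 and in the SAP".

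Section 11.5.2.1 then does four things:

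- It plans an unimputed summary: "Observed weekly ADPS and change from baseline will be summarized by CrCL group and week".
- It analyses each imputed dataset by repeated measures with "baseline ADPS as a covariate to provide LS mean in weekly ADPS at each week", and combines the results by Rubin's rule.
- It bounds dropouts for lack of efficacy, whose "imputed weekly ADPS after discontinuation cannot be better than that" subject's baseline.
- It lists sensitivity analyses: repeated measures on observed data, LOCF, and "ANCOVA using Baseline Observation Carried Forward".

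Section 11.5.2 places all efficacy analyses on the safety analysis set and rules out hypothesis tests.

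**The concern.** A responder rate needs a status for every subject in its denominator. Section 11.5.2.1 offers four possible sources for a missing Week 14 value: observed data only, multiple imputation, BOCF and LOCF. Section 11.5.2.2 chooses none of them and does not refer back. The only result that 11.5.2.1 draws from the imputed datasets is a set of least squares means. A literal reader could therefore drop subjects without Week 14 data, count them as failures or use the imputed values, and the report might not say which was done.

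The choice can move the rate. Under multiple imputation, a subject who stops for an adverse event can be a responder in some datasets; under BOCF that subject never is. The responder rate is a listed secondary endpoint, and results are shown by CrCL group. If a group held 5 to 10 subjects (assumed), one reclassified subject would move its rate by 10 to 20 points.

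**Working it through.** **1. Reading the sections together.** The rule in 11.2 covers weekly ADPS in general and is not tied to one model. Week 14 ADPS is a weekly ADPS, and responder status depends only on that value and baseline. Once the value is imputed, status is fixed in each dataset. Where the plan wants unimputed data it says so: the summary in 11.5.2.1 is labelled as observed, and so is the observed-data sensitivity analysis. Section 11.5.2.2 carries no such label. Its rates are also computed on the safety analysis set, which fits poorly with a rate among Week 14 completers.

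**2. Combining datasets.** The point estimate under Rubin's rule is the mean over imputations. For a proportion, that is the average of the per-dataset proportions. No test is planned, so no further pooling rule is needed.

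**3. The plan's own figure and the assumed dropout.** Section 11.11 asks for 30 subjects to see at least one event at a 10% rate with 95% probability: 1 − 0.9^30 = 95.8%, which reproduces. No dropout rate is stated. Enrolling 35 to keep 30 implies 5/35 = 14.3%, so 5 missing is the base assumption.

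**4. Simple bounds.** Assume 12 responders among 30 completers.

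| Handling of the 5 missing | Rate |
|---|---|
| Left out | 12/30 = 40.0% |
| Imputed at the completer rate | (12 + 5 × 0.4)/35 = 40.0% |
| All non-responders | 12/35 = 34.3% |
| All responders (extreme) | 17/35 = 48.6% |

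The exact 95% interval for 12/30 is 22.7% to 59.4%, wider than this whole range.

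**5. Simulation of the planned imputation.** Assumptions:

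- 35 subjects with 14 weekly values; baseline mean 5.5 or 6.5 (SD 1.2, limited to 4 to 8.9).
- Mean Week 14 reduction 1.9 or 2.8, within the range in Section 1.1.1.5.3, which comes from a 5-week study; SD 1.8 or 2.2; adjacent-week correlation 0.9.
- Last observed week uniform over 1 to 13.
- Predictive mean matching with 5 donors on baseline and the last two weeks, without age and sex.
- The plan's shifts (1.0, 1.0, 0.5) × RSD × U(0,1), cap at 10, and baseline bound for lack of efficacy (LOE).
- 10 imputations, and 250 trials in each of 8 settings per dropout count.

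Differences are in percentage points.

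| Dropouts (AE, LOE, other) | Threshold | Observed minus imputed | Imputed minus non-responder |
|---|---|---|---|
| 3 (2, 0, 1) | 30% | −0.2 to 0.4 | 3.9 to 6.3 |
| 3 (2, 0, 1) | 50% | 0.0 to 0.5 | 1.6 to 4.2 |
| 5 (3, 1, 1) | 30% | 1.6 to 2.0 | 5.2 to 8.3 |
| 5 (3, 1, 1) | 50% | 1.3 to 1.6 | 2.1 to 5.3 |
| 7 (4, 1, 2) | 30% | 1.6 to 1.9 | 7.8 to 12.6 |
| 7 (4, 1, 2) | 50% | 1.5 to 1.9 | 3.2 to 7.9 |

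Example (baseline 5.5, reduction 1.9, SD 1.8, 5 dropouts): the 30% rate is 45.5% non-responder, 51.3% imputed and 53.1% observed. The 50% rate is 25.5%, 28.5% and 29.8%.

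One subject in 35 is 1/35 = 2.9 points, so every gap between observed and imputed rates is below one subject.

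**6. Ceiling on the larger gap.** An LOE dropout's imputed value is no better than baseline, so that subject is never a responder. The imputed rate can exceed the non-responder rate by at most the other dropouts over 35: 3/35 = 8.6, 4/35 = 11.4 and 6/35 = 17.1 points in the three cases.

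**The case for a change.** The case for adding a sentence is a fair one. Use of the imputed values is inferred, not written. Status can differ between imputed datasets, yet 11.5.2.1 states pooling only for the model results. Section 11.5.2.2 does not name the week for the cumulative distribution. The denominator is not spelled out either: 11.2 limits change-from-baseline analyses to subjects with a baseline and at least one later value, while 11.5.2 uses everyone dosed. How adverse-event dropouts count matters to readers of a tolerability study, and one sentence would cost almost nothing.

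The omission stands as a matter of text. But averaging is the ordinary way to pool a proportion, and Week 14 is the only week named in the section. The denominator question affects only subjects with no post-baseline ADPS, and reported group counts would show it. That an adverse-event dropout may count as a responder follows from the imputation model the plan chose, so a cross-reference would not alter it. The effect of one subject in a small CrCL group reflects the group's size and holds under any rule. A separate non-responder rate would be an extra analysis by preference and would correct no wrong result.

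**Conclusion.** No change follows. The gap is one of detail, and analysts following Section 11.2 would fill it soundly: status from the imputed Week 14 ADPS, averaged over imputations. Confusing the two likeliest sources, observed and imputed data, would shift the rate by about 2 points or less, under one subject in 35. The larger differences, up to 12.6 points with 7 dropouts, arise only against a non-responder rule; the plan uses BOCF solely as a sensitivity analysis of mean ADPS. No test, error rate, sample size or safety conclusion depends on the choice.

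The sizes rest on assumed dropout numbers and reasons, variability and timing, and on pooling both CrCL groups. The SAP to which 11.2 defers, and the missing-data paper cited for the cumulative curve, could not be consulted; either may already state the rule. The conclusion does not depend on their doing so.

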#### **11.5.2.3 Short-Form McGill Pain Questionnaire**

For the sensory score, affective score, total score, VAS, and the present pain intensity index, the measured value and the change from baseline will be summarized at each scheduled visit.

#### **11.5.2.4 Patient Global Impression of Change**

PGIC score will be described as frequency table.

#### **11.5.2.5 Sleep-Interference Score**

The summary statistics will be computed for the ADSIS and the change from baseline at each week.

### **11.6 Pharmacokinetic/Biomarker Analyses**

#### **11.6.1 Pharmacokinetic Analyses**

Scatter plot illustrating the pharmacokinetic relationship between time after dose and plasma concentration by renal function for each visit will be created, using the PK

analysis set. The population PK analysis will be reported separately from the clinical study report (ie not in the clinical study report).

### **11.6.2 Biomarker Analyses**

Not applicable.

## **11.7 Safety Analyses**

### **11.7.1 Adverse Event Analyses**

All AEs will be coded using the Medical Dictionary for Regulatory Activities (MedDRA). Any AEs that appear after the first administration or that worsen relative to the pre-treatment state are considered as TEAEs.

The number and percentage of subjects reporting TEAEs will be calculated for the categories listed below by CrCL group and all-DS-5565 treatment. The number and percentage of subjects reporting TEAEs and ADRs will be summarized by system organ class, preferred term, and CrCL group and all-DS-5565 treatment.

- TEAE
- ADR
- Serious TEAE
- Serious ADR
- Severe TEAE
- Severe ADR
- Significant TEAE
- Significant ADR
- TEAE leading to treatment discontinuation
- ADR leading to treatment discontinuation

### **11.7.2 Clinical Laboratory Evaluation Analyses**

For the hematology and blood chemistry test parameters, summary statistics will be calculated for the measured values and change from baseline at each scheduled visit. A shift table will be created based on the categories of “abnormal low”, “normal”, and “abnormal high” between baseline and each scheduled visit.

Additionally, for ALT, AST, T-Bil, and ALP, the number and percentage of subjects who meet the criteria specified in FDA Drug-Induced Liver Injury guideline and evaluation of drug-induced serious hepatotoxicity plot will be provided. For the urinalysis parameters excepting specific gravity, the number and percentage of subjects will be provided at each visit. Summary statistics will be tabulated for the specific gravity. A shift table will be created based on the categories of “normal” and “abnormal” between baseline and each scheduled visit.

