### **1.3 Risks and Benefits for Study Subjects**

The clinical efficacy of DS-5565 has been established in 2 Phase 2, multi-center, randomized, double-blind, placebo-, and active-comparator controlled adaptive studies in subjects with DPNP. In DS5565-A-U201 conducted in the US, DS-5565 15 mg QD, 10 mg BID, and 15 mg BID treatment groups demonstrated statistically significant mean reductions in ADPS from baseline to end-of-treatment compared to placebo. In DS5565-A-J202 conducted in Asian countries, DS-5565, 5, 10, and 15 mg BID showed numerically mean reductions in ADPS, although the reductions were not statistically significant. The results were supportive of the US study. These data provide proof-of-concept for DS-5565 as a treatment for DPNP and suggest that DS-5565 may have utility in other chronic pain conditions, such as PHN and FM.

Anticipated risks of DS-5565 include the occurrence of adverse reactions related to CNS depression, such as dizziness and somnolence, as well as peripheral edema. Other notable TEAEs that have been observed in Phase 1 and Phase 2 studies include elevations of hepatic transaminases and suicide/suicidal ideation, both of which are carefully monitored and assessed as AESI in the ongoing Phase 3 DPNP, PHN, and FM programs. Ongoing monitoring of the Phase 3 program has identified no new safety concerns. For the approved  $\alpha_2\delta$  ligands, in addition to dizziness, somnolence, and peripheral edema, certain adverse reactions requiring caution have also been reported, including but not limited to: weight gain, ophthalmologic disorders, suicidal behavior and ideation, angioedema, hypersensitivity, abrupt or rapid discontinuation, abuse potential, congestive heart failure, renal failure, and creatine kinase elevations. Given the totality of clinical and nonclinical data, the current risk management approach appropriately safeguards subject safety, and the risk/benefit assessment is deemed positive.

In patients with moderate to severe renal impairment, sufficient efficacy of DS-5565 and acceptable risk of TEAEs on CNS are expected by the administration of the drug at an appropriate dosage based on the estimated exposure to the drug in those patients.

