#### **4.1.2 Inclusion Criteria**

Subjects must satisfy all of the following criteria to be included in the study.

For patients with DPNP and patients with PHN:

- 1) Age  $\geq$  20 years at informed consent
- 2) Able to give written informed consent for study participation, understand procedures of this study, and complete patient-reported questionnaires adequately
- 3) CrCL (using the Cockcroft-Gault equation): 15-59 mL/min at screening
- 4) At screening, a pain scale of  $\geq$  40 mm on VAS of SF-MPQ
- 5) At initiation of study treatment, a pain scale of  $\geq$  40 mm on VAS of SF-MPQ, and completion of at least 4 days of daily pain diaries with an ADPS of  $\geq$  4 over the past 7 days on the 11-point Numerical Rating Scale (NRS)

For patients with DPNP only:

- 6) Type 1 or type 2 diabetes mellitus at screening
- 7) Painful distal symmetric polyneuropathy, diagnosed at least 6 months prior to screening (see Procedures manual for the Diagnosis of Diabetic Peripheral Neuropathy and Neurological Examination for details)

For patients with PHN only:

- 8) PHN defined as pain present for 3 months or more after herpes zoster skin rash at screening

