#### **4.2.2 Reasons for Withdrawal**

If a subject discontinues from the study treatment for any reason, the date and the reason for discontinuation must be recorded in the Electronic Case Report Form (eCRF) using the following criteria.

For subjects withdrawn prior to randomization but after signing informed consent

- Screen failure
- Withdrawal by subject (eg, AE, Lack of efficacy [LOE], Other)
- Physician decision
- Other

For subjects withdrawn after the initiation of study treatment but before completing the study as per protocol

- AE
- Death
- LOE
- Lost to follow-up
- Protocol violation
- Decrease in CrCL < 15 mL/min
- Pregnancy
- Study terminated by sponsor
- Withdrawal by subject (eg, AE, LOE, Other)
- Other

If a subject is withdrawn due to need for a prohibited medication, the reason may be recorded as LOE, as appropriate. Reasons recorded under “Protocol violation” may include failure to comply with protocol requirements or study procedures.

For all subjects who withdraw from the study, the investigator must complete and report pertinent observations as thoroughly as possible up to the date of withdrawal, including the date of last treatment and the reason for withdrawal.

If a subject is withdrawn due to an AE, the investigator should follow the subject until the AE has resolved or stabilized.

All subjects who are withdrawn from the study should complete protocol-specified withdrawal procedures (see Section 4.2.3 and Section 6.4).

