### **9.4 Clinical Laboratory Evaluations**

The study site staff will collect blood and urine specimens for routine laboratory tests at specified times. Specimens will be stored under conditions stipulated in the Sample Handling Manual until they are transported for measurement. Specimens will be transported and measured by a central laboratory. Table 9-2 summarizes the laboratory parameters to be assessed and the times of assessment.

Results of all laboratory tests will be reported from the central laboratory to the site.

A value or finding that represents a clinically significant abnormal change should be regarded as an AE, and should be described (diagnosed) appropriately in the CRF.

Table 9-2: Laboratory Parameters to be Assessed, and Time of Assessment

	Parameters	Time of assessment
Hematology	WBC, RBC, hemoglobin, hematocrit, platelet count, differential leukocyte (neutrophil, eosinophil, basophil, monocyte, lymphocyte) counts, reticulocyte count	
Blood chemistry	Total protein, albumin, A/G ratio, T-Bil, AST (GOT), ALT (GPT), ALP, $\gamma$ -GT ( $\gamma$ -GTP), LDH, BUN, creatinine, uric acid, creatine kinase, total cholesterol, triglycerides, Na, K, Cl, Ca, Mg, inorganic phosphorus, bicarbonate, CRP	Visit 1, Visit 2, Visit 3, Visit 4, Visit 5, Visit 6, Visit 7, Visit 8, Visit 9, Visit 10, and Visit 11
Urinalysis	Standard urinalysis, including microscopic examination	
Pregnancy	Qualitative test (urine)	Visit 1 and Visit 10
HbA1c (only in patients with DPNP)	HbA1c	Visit 1, Visit 6, and Visit 10
Fasting blood glucose (only in patients with DPNP)	Fasting blood glucose level	Visit 1, Visit 6, and Visit 10

A/G ratio = albumin/globulin ratio CRP = C-reactive protein, LDH = lactate dehydrogenase, RBC = red blood cell, WBC = white blood cell

As described in Section 4.2.1, increases in aminotransferases have been observed in the DS-5565 development program to date. Special monitoring of such elevations during Phase 3 is described below. The Hepatic Adjudication Committee (HAC) charter includes a process by which selected cases will be adjudicated by a liver disease specialist (Section 11.10). In cases of liver laboratory abnormalities, it is important to

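### The creatinine shift table in Section 11.7.2 has a ceiling for subjects already above normal at baseline, and no planned output counts worsening relative to baseline or summarises CrCL on treatment

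*Combined protocol and SAP*

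**What the plan says.** Section 4.1.2 admits subjects on "CrCL (using the Cockcroft-Gault equation): 15-59 mL/min at screening". Creatinine is in the blood chemistry panel (Section 9.4, Table 9-2: "LDH, BUN, creatinine, uric acid, creatine kinase") at every visit from Visit 1 to Visit 11. Body weight is also measured at every visit (Section 9.7.1). CrCL is not a listed laboratory parameter.

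Section 11.7.2 gives the hematology and chemistry parameters two outputs. The first is numerical: "summary statistics will be calculated for the measured values and change from baseline at each scheduled visit". The second is categorical, from baseline to each scheduled visit: "A shift table will be created based on the categories of “abnormal low”, “normal”, and “abnormal high". Only ALT, AST, T-Bil and ALP get a further count of subjects meeting set criteria. Section 11.2 defines the summary statistics as mean, SD, median, minimum, maximum and number of observations, and states: "All analyses will be conducted by CrCL group".

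Three other routes touch renal worsening. "Decrease in CrCL < 15 mL/min" is a withdrawal criterion (Section 4.2.1) and a recorded reason (Section 4.2.2). Section 9.4 makes a clinically significant abnormal laboratory change an adverse event. Section 11.7.1 counts subjects with treatment-emergent events, including those that worsen from the pre-treatment state.

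**The concern.** The primary objective is safety in moderate to severe renal impairment, and CrCL defines the population, the analysis groups and a withdrawal criterion. Section 1.3 lists "congestive heart failure, renal failure, and creatine kinase elevations" among the reactions requiring caution with the approved drugs of the class. Section 1.2 says that exposure to DS-5565 depends on renal function.

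The entry criterion selects subjects who tend to have raised creatinine. For anyone above the ULN at baseline, the low/normal/high scale has no higher level, so an unchanged category could reflect the scale rather than stable kidneys. At stake is whether the report can say how many of the approximately 35 subjects lost a material part of their renal function, and whether adverse events can be read against that loss.

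**Working it through.** Section 11.7.2 has no figure to reproduce. The plan's only design calculation (Section 11.11) is not affected by this point. It does reproduce: 1 - 0.9^29 = 95.3% and 1 - 0.9^30 = 95.8%, in line with the stated 30 subjects.

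**1. Inputs.** From the documents: entry CrCL 15-59 mL/min; groups 30-59 (moderate) and 15-29 (severe); the Cockcroft-Gault equation is named but not printed. Assumed, because the documents do not give them: creatinine ULN 0.9-1.3 mg/dL for men and 0.7-1.1 for women; age 60-88 years; weight 50-75 kg for men and 40-65 kg for women; each of age, weight and CrCL uniform within its range.

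**2. Formula.** Creatinine = (140 - age) x weight x (0.85 if female) / (72 x CrCL).

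**3. Share of subjects above the ULN at entry** (200,000 simulated subjects per group and sex; the first ULN is the lowest assumed, the last the highest):

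| Group | ULN, mg/dL | Share above ULN |
|---|---|---|
| Severe men | 0.9 to 1.3 | 100% throughout |
| Severe women | 0.7 to 1.1 | 100% up to 1.0; 98% at 1.1 |
| Moderate men | 0.9, 1.0, 1.1, 1.2, 1.3 | 92%, 83%, 72%, 60%, 48% |
| Moderate women | 0.7, 0.8, 0.9, 1.0, 1.1 | 84%, 69%, 53%, 38%, 26% |

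**4. What the shift table would show in three cases.**

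- Severe man, 70 years, 60 kg: 70 x 60 / 72 = 58.33. At creatinine 2.1, CrCL = 58.33 / 2.1 = 27.8; at 3.8, CrCL = 58.33 / 3.8 = 15.4. Creatinine rises by 1.7 mg/dL (1.81-fold) and CrCL falls 45%. The table reads high to high, and CrCL is not below 15.
- Moderate man, same age and weight, CrCL 40 to 20: creatinine 58.33 / 40 = 1.46 to 58.33 / 20 = 2.92, a rise of 1.46 mg/dL and a 50% fall in CrCL. He crosses from the moderate to the severe range, yet reads high to high at every assumed ULN.
- Moderate woman, 80 years, 50 kg, CrCL 50 to 30: 60 x 50 x 0.85 / 72 = 35.42; creatinine 35.42 / 50 = 0.71 to 35.42 / 30 = 1.18, a rise of 0.47 mg/dL and a 40% fall in CrCL. She reads normal to high for any ULN from 0.8 to 1.1, so here the table works.

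**5. Whether the mg/dL summaries fill the gap.** The two moderate cases lose 50% and 40% of CrCL, with creatinine changes of 1.46 and 0.47 mg/dL. The group maximum would show only the first. A change in mg/dL does not translate into a fixed loss of function, and a maximum does not say how many subjects worsened.

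**6. Room below the withdrawal criterion.** A fall from 29 to just above 15 mL/min is a loss of up to 1 - 15/29 = 48%. It would trigger neither a shift nor the withdrawal reason.

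**The case against.** The case on the other side is substantial. Renal worsening is not left unanalysed. Creatinine change from baseline is summarised at each visit by CrCL group, with the maximum, so a rise of 1.7 mg/dL in one severe subject could not vanish: that group's maximum would be at least 1.7. A clinically significant change is an adverse event and is counted per subject. A fall below 15 mL/min has its own withdrawal reason. Renal failure is listed for the approved drugs of the class, not as an observed or anticipated risk of DS-5565. The liver parameters get extra counts because hepatic events are of special interest in this programme. Section 11.2 also defers detail to a separate SAP, whose text is not in the document reviewed, so only absence from the protocol is shown.

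Most of this stands, and it rules out three stronger readings that a reader might infer:

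- That the shift table cannot show renal worsening at all. Under the assumptions above, 8-52% of moderate men and 16-74% of moderate women start within the normal range and can shift to high.
- That the table is the only per-subject readout. Adverse event counts and the withdrawal reason are per-subject too.
- That BUN and urinalysis saturate in the same way. The documents give no reference limits for BUN and no baseline urinalysis findings, so neither can be shown.

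What the objection does not answer is the count. Adverse event capture depends on the investigator's judgement, the withdrawal reason sees only one fixed threshold, and the numerical summaries give no number of subjects.

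**Conclusion.** The point holds as a reporting gap. For subjects with creatinine above the ULN at baseline, the shift table cannot register a further rise. That is practically all of the severe group (98-100%) and an uncertain share of the moderate group (26-92% across sex and assumed ULN). These shares rest on assumed ULN, age, weight and a uniform CrCL distribution. The conclusion for the severe group is stable across the ranges tried; the one for the moderate group is not.

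The other planned outputs would reveal part of the deterioration. Even so, nothing in Sections 11.2 to 11.8 counts subjects whose renal function worsened by a set amount relative to baseline, or summarises CrCL on treatment. Sample size and data collection are unaffected, and no hypothesis test is involved. Because the gap bears on the primary safety objective and is cheap to close, it should be closed.

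**What to change.** Keep the low/normal/high shift table for creatinine, since it works for subjects who start within the normal range. Add to Section 11.7.2 (and carry into the SAP), by CrCL group:

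- (a) the number and percent of subjects by maximum on-treatment creatinine relative to their own baseline, for example at least 1.5 times and at least 2 times. These are conventional reporting cut-offs, not taken from the documents and not rules for managing subjects.
- (b) Cockcroft-Gault CrCL and its percent change from baseline by visit, with a shift across 30-59, 15-29 and below 15 mL/min.

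Calculate CrCL with baseline body weight, or show both versions. The equation is proportional to weight, and edema and weight increase are named significant adverse events (Section 9.1.1). A gain from 60 to 63 kg alone raises computed CrCL by 63/60 - 1 = 5% and would mask some decline.

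Both parts are needed. With weight and age held fixed, creatinine ratios of 1.5 and 2 correspond to CrCL falls of 1 - 1/1.5 = 33% and 1 - 1/2 = 50%. A subject with baseline CrCL in 15-29 cannot reach a ratio of 2 without going below 15 (29/15 = 1.93), so in the severe group the 1.5-fold count and the percent change carry most of the information.

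The cost is one extra descriptive table and a few lines of wording. Creatinine and weight are already collected at every visit, so no sample, visit or form changes. The downside is that the cut-offs are conventional and, with about 35 subjects, the counts will be small and purely descriptive.
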